## 7.2 STUDY CALENDAR: ATEZOLIZUMAB (CROSSOVER)

Crossover therapy (atezolizumab) must begin no later than 21 days after the clinic visit at which progression is determined.

Procedure	Cycle 1 a (21-days)	Additional cycles a	End-of-treatment c	30 day follow-up b	1, 2, 3 year follow-up i
	Day 1	Day 1			
Physical exam/signs and symptoms c	X	X	X		
Vital signs (including oxygen sat)	X	X	X		
ECOG Performance Status	X	X	X		
Blood collection	Clinical laboratory tests d	X	X		
	TSH, free T3, T4 e	X		X (every 4 th cycle)	
	Circulating tumor DNA	X	X (Cycle 2 only)	X	
	Mononuclear Cell Collection	X	X (Cycle 2 only)	X	
Tumor assessment CTs, bone scan f		X (every 3 cycles)			
Tumor biopsy (metastatic site) at crossover g	X				
Atezolizumab administration (IV)	X	X			
Concomitant medications h	X	X			
Adverse events	X	X		X	X i

- Evaluation assessments should be performed prior to administration of IMP unless otherwise indicated. Results should be reviewed by the Investigator prior to the administration of the next dose. All visits should occur within 3 days of scheduled visit unless otherwise noted. Delays up to 7 days will be considered by study chair. Crossover therapy (atezolizumab) must begin no later than 21 days after the clinic visit at which progression is determined. Exceptions must be discussed with the Protocol Chair.
- The 30-day follow-up assessments should be done 30 (±3 days) days after the last dose of study drugs. 30 day follow-up can be done by phone or by a clinic visit. Any ongoing toxicities should be documented. Any ongoing serious adverse events will be followed every 3 months until resolution. Any AEs or SAEs considered possibly or probably related to IMP that have not stabilized, returned to baseline, or are considered irreversible will continue to be monitored as per the protocol.
- The physical examination will include measurements of height and weight at screening. Weight will be measured on day 1 of each cycle and at the End-of-treatment visit. Physical examination will include examination of major body systems including neurologic, cardiac, respiratory, gastrointestinal, and skin. Clinically relevant signs and symptoms will be reported as AEs.
- Clinical laboratory tests will include hematology and serum chemistry panel including white blood cell count, differential, hemoglobin, platelet count, sodium, potassium, chloride, bicarbonate, BUN, creatinine, glucose, calcium, and magnesium, AST (SGOT), ALT (SGPT), and total serum bilirubin, albumin, and total protein. Additional tests will be performed when clinically appropriate. In case of Grade 3 or higher abnormal AST/ALT, additional testing will be done weekly until recovery to baseline value. Labs can be performed up to 3 days prior to each timepoint indicated in the study calendar.
- See section 9.1.4 for abnormal results

- f Tumor assessment should be performed approximately every 3 cycles (up to -5 days) while on study treatment and at End-of-treatment visit if not obtained within the past 6 weeks. Scans should consist of CT scan of the chest, abdomen, and pelvis and a bone scan at baseline. Subsequent scans should consist of CT chest, abdomen and pelvis, and bone scan if bone metastases were present on the baseline studies. At the end of treatment, all scans (baseline and through disease progression) should be sent on a CD to the Vanderbilt Cancer Imaging Support Laboratory for central review and assessment. See Section 12 for details and address.
- g Tumor biopsies from a metastatic site will be obtained from patients prior to day 1 (this will be the biopsy obtained at disease progression on the carboplatin only arm).
- h The dose of steroids before each carboplatin injection should be recorded. See protocol for concomitant medications that are prohibited (section 8).
- i 1, 2, and 3 year follow-up can be done by phone or chart review to document survival status, and if applicable, the date of death and cause of death. Surveillance for Adverse Events of Special Interest (AESIs) – see section 13.5.12 should be included.

## 8. TREATMENT PLAN

### 8.1 Overview

This is an open-label phase II multi-institution trial that evaluates the safety profile and anti-tumor activity of carboplatin +/- atezolizumab in patients with metastatic triple negative (ER negative, PR negative, HER2neu negative by IHC or FISH) breast cancer. Patients will be treated with carboplatin AUC 6 IV on day 1 and atezolizumab 1200 mg IV on day 1 of a 21 day cycle or carboplatin AUC 6 IV on day 1 of a 21 day cycle. For patients on the combination arm, atezolizumab is to be administered prior to carboplatin. For patients on the combination arm, carboplatin can be stopped after cycle 6 and atezolizumab can be continued as a single-agent at the discretion of the treating physician.

### 8.2 Concomitant Treatment and Supportive Care Guidelines

#### 8.2.1 Concomitant Therapy

Concomitant therapy includes any prescription medications or over-the-counter preparations used by a patient between the 7 days preceding Cycle 1, day 1 and the treatment discontinuation visit.

Neulasta (pegfilgrastim) may be given prophylactically per treating investigator discretion.

Patients who experience infusion-associated symptoms may be treated symptomatically with acetaminophen, ibuprofen, diphenhydramine, and/or cimetidine or another H2 receptor antagonist, as per standard practice. Serious infusion-associated events manifested by dyspnea, hypotension, wheezing, bronchospasm, tachycardia, reduced oxygen saturation, or respiratory distress should be managed with supportive therapies as clinically indicated (e.g., supplemental oxygen and  $\beta_2$ -adrenergic agonists).

Systemic corticosteroids and TNF $\alpha$  inhibitors may attenuate potential beneficial immunologic effects of treatment with atezolizumab but may be administered at the discretion of the treating physician. If feasible, alternatives to corticosteroids should be considered. The use of inhaled corticosteroids and mineralocorticoids (e.g., fludrocortisone) for patients with orthostatic hypotension or adrenocortical insufficiency is allowed. Megastrol administered as appetite stimulant is acceptable while the patient is enrolled in the study.

Patients who use prophylactic or therapeutic anticoagulation therapy (such as low-molecular-weight heparin or warfarin at a stable dose level), or other allowed maintenance therapy can continue their use. Males and females of reproductive potential should use highly effective means of contraception.

### 8.2.2 Excluded Therapy

Any concomitant therapy intended for the treatment of cancer, whether health authority-approved or experimental, is prohibited. This includes but is not limited to the following:

- Chemotherapy, hormonal therapy, immunotherapy, radiotherapy, investigational agents, or herbal therapy
  - After Cycle 1, certain forms of radiotherapy may be considered for pain palliation if patients are deriving benefit (e.g., treatment of known bony metastases); atezolizumab administration may be suspended during radiotherapy.

Patients must discontinue:

- Traditional herbal medicines because the ingredients of many herbal medicines are not fully studied and their use may result in unanticipated drug-drug interactions that may cause, or confound assessment of, toxicity
- The use of a RANKL inhibitor (denosumab); this agent could potentially alter the activity and the safety of atezolizumab. Bisphosphonates may be used in lieu of RANKL inhibitors.

Patients are not allowed to receive immunostimulatory agents, including but not limited to IFN- $\alpha$ , IFN- $\gamma$ , or IL-2, during the entire study. These agents, in combination with atezolizumab, could potentially increase the risk for autoimmune conditions.

Patients should also not be receiving immunosuppressive medications, including but not limited to cyclophosphamide, azathioprine, methotrexate, and thalidomide. These agents could potentially alter the activity and the safety of atezolizumab. Systemic corticosteroids and anti-TNF $\alpha$  agents may attenuate potential beneficial immunologic effects of treatment with atezolizumab but may be administered during the course of treatment at the discretion of the treating physician after discussion with the Protocol Chair. If feasible, alternatives to these agents should be considered.

In addition, all patients (including those who discontinue the study early) should not receive other immunostimulatory agents for 10 weeks after the last dose of atezolizumab.

### 8.3 Assessments during Treatment

All visits must occur within  $\pm 3$  days from the scheduled date, unless otherwise noted. Please see the Study Calendar at the beginning of this protocol for the schedule of treatment period assessments.

### 8.4 Cross-over post-progression

Patients who are randomized to carboplatin alone can cross over to receive atezolizumab upon disease progression based on clinical progression or radiographic progression. Patients who are randomized to carboplatin alone and who discontinue carboplatin for toxicity cannot cross over to receive single agent atezolizumab. There may be exceptions to this based on discussion with the Protocol Chair. However, patients on the carboplatin + atezolizumab arm can continue to receive single agent atezolizumab if they discontinue carboplatin due to toxicity. Patients who cross over to receive atezolizumab will follow the assessments and procedures as outlined in the study calendar. The duration of each cycle will continue to be 21

days and the cycle numbers will "reset" to 1 and will be followed by the "X" suffix (e.g., Cycles 1X, 2X, etc.). Crossover therapy (atezolizumab) must begin no later than 21 days after the clinic visit at which progression is determined.

Patients must have labs and procedures performed as outlined in the cross-over study calendar and must meet the values as described in the Inclusion Criteria, prior to receiving atezolizumab based on assessments and procedures performed within 21 days prior to Day 1 of Cycle 1X. Labs and procedures not included in the cross-over study calendar do not have to be repeated. Patients must also agree to a tumor biopsy, as outlined in the eligibility criteria, prior to initiating atezolizumab. Patients will receive crossover treatment until progression, intolerable toxicity, or elective withdrawal from the study. Patients who cross over will be evaluated with radiologic assessments every 3 cycles until disease progression.

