## 5.2 Exclusion Criteria

Patients who meet any of the following criteria will be excluded from registration:

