### *Cancer-Specific Exclusion Criteria*

- Spinal cord compression not definitively treated with surgery and/or radiation, or previously diagnosed and treated spinal cord compression without evidence that disease has been clinically stable for > 2 weeks prior to randomization
- Known CNS disease, except for treated asymptomatic CNS metastases, provided all of the following criteria are met: measurable disease outside the CNS, only supratentorial and cerebellar metastases are allowed (i.e., no metastases to midbrain, pons, medulla, or spinal cord), no evidence of progression or hemorrhage after completion of CNS-directed therapy, no ongoing requirement for dexamethasone as therapy for CNS disease (anticonvulsants at a stable dose are allowed), no stereotactic radiation within 7 days or whole-brain radiation within 14 days prior to randomization.
- Leptomeningeal disease
- Uncontrolled tumor-related pain: patients requiring narcotic pain medication must be on a stable regimen at registration. Symptomatic lesions (e.g., bone metastases or metastases causing nerve impingement) amenable to palliative radiotherapy should be treated prior to randomization. Patients should be recovered from the effects of radiation. There is no required minimum recovery period. Asymptomatic metastatic lesions whose further growth would likely cause functional deficits or intractable pain (e.g., epidural metastasis that is not presently associated with spinal cord compression) should be considered for loco-regional therapy if appropriate prior to randomization.
- Uncontrolled hypercalcemia (> 1.5 mmol/L ionized calcium or calcium > 12 mg/dL or corrected serum calcium > ULN) or symptomatic hypercalcemia requiring continued use of bisphosphonate therapy. Patients who are receiving denosumab must discontinue denosumab use and replace it with a bisphosphonate instead while on study. Patients receiving a bisphosphonate for skeletal metastases are not excluded and can continue treatment.
- Malignancies other than TNBC within 5 years prior to randomization, with the exception of those with a negligible risk of metastasis or death and treated with expected curative outcome (such as adequately treated carcinoma in situ of the cervix or basal or squamous cell skin cancer).
- Concurrent anti-cancer therapy (chemotherapy, radiation therapy, surgery, immunotherapy, hormonal therapy, biological therapy) other than the ones specified

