### *General Medical Exclusion Criteria*

- Women only: pregnancy or lactation
- Evidence of significant uncontrolled concomitant disease that in the opinion of the investigator could affect compliance with the protocol or interpretation of results, including significant liver disease (such as cirrhosis, uncontrolled major seizure disorder, or superior vena cava syndrome)
- Significant cardiovascular disease, such as New York Heart Association (NYHA) cardiac disease (Class II or greater), myocardial infarction within 3 months prior to randomization, unstable arrhythmias, or unstable angina. Patients with a known left ventricular ejection fraction (LVEF) < 40% will be excluded. Patients with known coronary artery disease, congestive heart failure not meeting the above criteria, or LVEF < 50% must be on a stable medical regimen that is optimized in the opinion of the treating physician, in consultation with a cardiologist if appropriate.
- Severe infection requiring systemic treatment within 4 weeks prior to randomization, including but not limited to hospitalization for complications of infection, bacteremia, or severe pneumonia
- Major surgical procedure within 4 weeks prior to randomization or anticipation of the need for a major surgical procedure during the course of the study other than for diagnosis. Placement of central venous access catheter(s) (e.g., port or similar) is not considered a major surgical procedure and is therefore permitted.
- History of severe reactions (e.g. allergic, anaphylactic, or other hypersensitivity) to chimeric or humanized antibodies or fusion proteins
- Known hypersensitivity or allergy to biopharmaceuticals produced in Chinese hamster ovary cells or any component of the atezolizumab formulation
- History of autoimmune disease, including but not limited to myasthenia gravis, myositis, autoimmune hepatitis, systemic lupus erythematosus, rheumatoid arthritis, inflammatory bowel disease, vascular thrombosis associated with antiphospholipid syndrome, Wegener's granulomatosis, Sjögren's syndrome, Guillain-Barré syndrome, multiple sclerosis, vasculitis, or glomerulonephritis. Patients with a history of autoimmune-related hypothyroidism on a stable dose of thyroid replacement hormone are eligible for this study. Patients with controlled Type 1 diabetes mellitus on a stable insulin regimen are eligible for this study.

- Prior allogeneic stem cell or solid organ transplantation

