- History of idiopathic pulmonary fibrosis (including pneumonitis), drug-induced pneumonitis, organizing pneumonia (i.e., bronchiolitis obliterans, cryptogenic organizing pneumonia), or evidence of active pneumonitis on screening chest CT scan. History of radiation pneumonitis in the radiation field (fibrosis) is permitted.
- Positive test for HIV (testing required prior to registration)
- Active hepatitis B (defined as having a positive hepatitis B surface antigen [HBsAg] test at screening) or hepatitis C
- Patients with past hepatitis B virus (HBV) infection or resolved HBV infection (defined as having a negative HBsAg test and a positive antibody to hepatitis B core antigen [anti-HBc] antibody test) are eligible.
- Patients positive for hepatitis C virus (HCV) antibody are eligible only if polymerase chain reaction (PCR) is negative for HCV RNA.
- Active tuberculosis
- Receipt of a live, attenuated vaccine within 4 weeks prior to initiation of study drug (C1D1) or anticipation that such a live, attenuated vaccine will be required during the study
- Prior treatment with CD137 agonists, anti-PD-1, or anti-PD-L1 therapeutic antibody or pathway-targeting agents
- Treatment with systemic immunostimulatory agents (including but not limited to interferons or IL-2) within 4 weeks or five half-lives of the drug (whichever is shorter) prior to randomization
- Treatment with systemic corticosteroids or other systemic immunosuppressive medications (including but not limited to prednisone, dexamethasone, cyclophosphamide, azathioprine, methotrexate, thalidomide, and anti-tumor necrosis factor [TNF] agents) within 2 weeks prior to cycle 1, day 1, or anticipated requirement for systemic immunosuppressive medications during the trial. Patients who have received acute, low-dose, systemic immunosuppressant medications (e.g., a one-time dose of dexamethasone for nausea) may be enrolled in the study. Patients on a stable low dose ( $\leq 10$  mg) daily prednisone or equivalent are allowed on study. Patients with a history of allergic reaction to IV contrast requiring steroid pre-treatment should have baseline and subsequent tumor assessments performed using MRI. The use of inhaled corticosteroids for chronic obstructive pulmonary disease, mineralocorticoids (e.g., fludrocortisone) for patients with orthostatic hypotension, and low-dose supplemental corticosteroids for adrenocortical insufficiency are

allowed.

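### Crossover entry in Section 8.4 does not re-apply the Section 5.2 exclusions, and the crossover calendar has no pregnancy test before a control patient's first atezolizumab dose

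*Combined protocol and SAP*

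**What the plan says.** Section 8.4 lets patients randomized to carboplatin alone cross over at clinical or radiographic progression, on these conditions:

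- Patients "who discontinue carboplatin for toxicity cannot cross over to receive single agent atezolizumab", although exceptions can be discussed with the Protocol Chair.
- Atezolizumab starts within 21 days of the visit at which progression is determined.
- Patients have the crossover-calendar labs and procedures within 21 days before Cycle 1X Day 1 and "must meet the values as described in the Inclusion Criteria, prior to receiving atezolizumab".
- The patient agrees to a tumor biopsy. The reference to the eligibility criteria in that sentence concerns the biopsy only.

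It then adds a waiver: "Labs and procedures not included in the cross-over study calendar do not have to be repeated".

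Section 5.2 opens with "Patients who meet any of the following criteria will be excluded from registration". Several of its items are tied to study entry, such as "Severe infection requiring systemic treatment within 4 weeks prior to randomization" and "evidence of active pneumonitis on screening chest CT scan". The live-vaccine item counts 4 weeks back from Cycle 1 Day 1 and also excludes patients expected to need such a vaccine during the study. Known CNS disease is excluded unless it is treated and asymptomatic and meets further conditions, among them "no evidence of progression or hemorrhage after completion of CNS-directed therapy".

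In the 7.1 calendar the serum pregnancy test appears at screening only. Footnote f waives it for patients aged 55 or over, known to be postmenopausal, or with a hysterectomy. The 7.2 crossover calendar has no pregnancy test, either as a row or in its laboratory footnote.

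**The concern.** A control patient first meets atezolizumab at Cycle 1X, after a period on carboplatin and just after the disease has progressed. The exclusions that guard against starting this drug were judged once, at registration. A condition that arose since then is outside their wording, and 8.4 does not bring them forward.

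Elsewhere the protocol does care about how current screening is. Section 6.1 sends a patient back to screening if treatment does not start in the allowed time, and 7.1 footnote b repeats history, examination and labs that are more than 7 days old at Cycle 1. Section 12 lets a combination patient stay on study past RECIST progression only if, among other things, there is no progression at critical sites, with leptomeningeal disease as its example. Crossover has no matching condition.

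What is at stake is patient safety and even handling across sites. Two sites could read the same text and treat the same patient differently. An unrecognized pregnancy could also be exposed to a first dose of atezolizumab because the only scheduled test predates carboplatin.

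**Working it through.** **Exclusions.** No arithmetic applies, so the entry rule is set against 5.2, item by item, for a condition that arises after registration.

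| New condition | What may reveal or stop it at Cycle 1X | What is left without a stated bar |
|---|---|---|
| Leptomeningeal or unstable CNS disease | Physical exam including neurologic; ECOG 0-1, if read as an Inclusion value | The condition itself |
| Active pneumonitis | Respiratory exam, oxygen saturation; 9.2.5 withholds at Grade 2 and discontinues at Grades 3-4, if those on-treatment rules are applied to a first dose | Grade 1, where 9.2.5 continues the drug with monitoring |
| Autoimmune disease | Exam including skin, adverse-event review; 9.2 covers some events (9.2.10 stops the drug for myasthenia gravis and Guillain-Barré syndrome); 8.2.2 rules out azathioprine, methotrexate and similar drugs | For example, new rheumatoid arthritis or lupus not treated with a prohibited drug |
| Severe infection within 4 weeks | Labs, adverse-event review; the 8.4 toxicity bar, if the event ended carboplatin | Infection that did not end carboplatin |
| Live vaccine within 4 weeks | Medication review; anticipated need was already screened at entry | An unanticipated vaccine; 8.2.2 does not mention vaccines |

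Two areas already have rules. Section 8.2.2 prohibits immunostimulatory agents throughout the study, and a known pregnancy leads to stopping study drug (8.7, 13.5.7).

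**Age of the pregnancy test at first atezolizumab.** Inputs:

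- Screening window: up to 28 days before dosing (7.1 footnote b).
- Cycle length: 21 days (8.1).
- First scan: on or up to 5 days before Cycle 4 Day 1 (7.1 footnote i).
- Crossover window: up to 21 days (8.4).

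Steps, for crossover at the first scheduled scan:

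1. Cycle 4 Day 1 falls 3 × 21 = 63 days after Cycle 1 Day 1. The earliest scan is at 63 − 5 = 58 days.
2. Shortest age without delays: 0 + 58 + 0 = 58 days.
3. Longest age without delays: 28 + 63 + 21 = 112 days, or 16 weeks.
4. With one 3-week carboplatin delay before Cycle 4 (allowed by 9.3.1.1): 112 + 21 = 133 days, or 19 weeks.
5. Combination arm: at most 28 days at the first atezolizumab dose. At Cycle 4 Day 1 it can be 28 + 63 = 91 days, with no retest.

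The ±3-day visit windows and exceptions to the 21-day window are not added, so 133 days is not an upper bound. Crossover after clinical progression before the first scan would give a younger test than 58 days.

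**The case against.** The strongest reply is that a crossover patient is far from unexamined. On Cycle 1 Day 1 the 7.2 calendar requires an exam covering the neurologic, cardiac, respiratory, gastrointestinal and skin systems, vital signs with oxygen saturation, ECOG, labs, and review of adverse events and medications. These come before dosing, with results reviewed by the investigator. The laboratory footnote allows extra tests, Section 9.2 asks for clinical assessment before each infusion, and 8.7 lets the investigator withdraw a patient for any medical condition that may jeopardize safety. On this view the change mostly writes down judgment that is already expected, and it could deny optional treatment to patients with progressing metastatic disease.

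Much of that stands. A reader might infer that 8.4 admits anyone with any condition listed in 5.2, or that crossover patients go unchecked. The documents do not support either: the required checks are substantial, 8.2.2 limits several drugs, and 9.2 covers the higher-grade pulmonary events and some autoimmune ones. What the reply does not supply is a rule. The checks can find a problem, but for the conditions left in the table nothing states that the first dose must be withheld.

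On pregnancy, the reply is that neither arm is retested and that a combination patient's test also grows old. That is right, and it confines the contrast to the first dose. A reader might also infer that the protocol permits atezolizumab in pregnancy. It does not: contraception is an entry requirement in 5.1, and a known pregnancy stops study drug. The gap is in detection only.

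**Conclusion.** The point holds as a cheap improvement for patient safety. Section 8.4 leaves a limited set of newly arisen, atezolizumab-relevant conditions without a stated bar to a first dose. The only scheduled pregnancy test is about 58 to 112 days old at that dose, assuming crossover at the first scheduled scan and no delays, against at most 28 days in the combination arm. The test matters only for patients outside the 7.1 waiver.

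The number affected cannot be derived, because the documents give no crossover rate, no rate of new exclusions and no count of patients of childbearing potential. The planned control arm of 53 (17.2) is a ceiling and not an estimate.

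A reader might infer that this also disturbs the efficacy result. The primary PFS comparison is unaffected, because crossover comes after progression.

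**What to change.** In 8.4, require the investigator to re-confirm before Cycle 1X those 5.2 exclusions that can newly arise and bear on atezolizumab safety, with time windows counted back from Cycle 1X Day 1. The list should hold at least leptomeningeal or unstable CNS disease, active pneumonitis, autoimmune disease, severe infection within 4 weeks and live vaccine within 4 weeks. Others of the same kind, such as myocardial infarction within 3 months or active tuberculosis, can join it. The re-check can use the exams and scans already planned, so no extra imaging is needed. The laboratory limits need no new text, since 8.4 already requires the Inclusion values.

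In 7.2, add that checklist row and a serum pregnancy test at Cycle 1 Day 1, with the same waiver as 7.1.

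The cost is one amendment to 8.4 and 7.2, one checklist row, and one routine test on blood already being drawn. The downside is that a few patients may not qualify for crossover.
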